4.3.6 Safety Analysis

Safety data, including ECOG performance status, vital signs, ECGs, heart ECHOs, clinical laboratory tests, physical examinations, lung X-rays, AEs, and ocular examinations, will be summarized by scheduled visits, as appropriate. Change from baseline will be included in summary tables for laboratory, ECG, and vital sign parameters. AEs will be coded by MedDRA and then summarized by system organ class and preferred term for each treatment.

4.3.6.1 Adverse Events

Subjects will be assessed for AEs at each scheduled clinic visit while on the study. All AEs reported on or after the date of first dose until 30 days (inclusive) after the last dose of study drug will be considered treatment-emergent adverse events (TEAEs) and will be summarized by treatment group. For each treatment group, TEAE incidence rates will be summarized with frequency and percentage by System Organ Class (SOC) and preferred term (PT), with safety subjects of that treatment group as the denominator, unless otherwise specified. In addition, TEAE incidence rates will also be summarized by maximum severity (CTCAE Grade) and relationship to study drug. Treatment-related AEs are those judged by the Investigator to be probably, possibly, or definitely related to the study drug. TEAEs with missing severity or relationship to study drug will be classified as severe and treatment-related, respectively. Subjects with multiple occurrences of events will only be counted once at the maximum severity to study drug for each preferred term, SOC, and overall. Deaths that occur within 30 days after the last dose of study drug are defined as on-study deaths.

Summary tables of the following TEAEs will be provided:

Overall summary of TEAEs: the number and percentage of subjects who experienced any TEAE, severe TEAE, serious adverse event (SAE), any related TEAE, related severe TEAE, related SAE, TEAE leading to treatment discontinuation, and AE leading to death

- TEAEs by SOC and PT
- TEAEs by SOC, PT, and maximum severity
- Related TEAEs by SOC and PT

Protocol P1101 in Japanese PV (A19-201)

- TEAEs that led to study drug discontinuation by SOC and PT. Study drug discontinuation will be determined from the AE case report form where action taken is drug withdrawn or etc.
- Serious TEAEs by SOC and PT
- General overview of TEAEs by 3 month periods

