4.1.4 Safety Population

The Safety Population will include all subjects who have received at least one dose of study drug. For this single arm study, ITT and safety populations are identical.

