4.3.1.1 Descriptive statistics

For categorical data (e.g. response to treatment: responder) standard set of summary statistics will be counts and percentages. Missing, unknown, not available, not applicable or not done categories will be included; therefore, the percentages will be calculated of total number of patients in the set. This approach was selected because it is close to intent-to-treat principle.

For continuous data (e.g. level of lymphocytes) the following descriptive statistics will be presented: number of available observations, mean, standard deviation (SD), median, interquartile range (IQR: Q1-Q3), minimum, and maximum.

Confidence intervals will be present if appropriate.

For time-to-event data (e.g. Time to first peripheral blood count response) KM method will be used for estimating the distribution, median with 95% CI will be presented.

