- Spleen size measurements by sonography will be summarized by scheduled time points, as appropriate.
- Difference in CHR rate between subject with or without of prior treatment with HU
- Proportion of subjects without thrombotic or hemorrhagic events

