4.3.5.4 Number of phlebotomies

Number of phlebotomies during treatment phase will be summarized using descriptive statistics and frequency/percentage for categories of 0,1,2,3 and >3.

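### The 3-month TEAE overview keeps patients in the denominator after they can no longer contribute a TEAE, so late-period percentages are understated in proportion to withdrawals

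*SAP*

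**What the plan says.** **TEAE rates.** SAP 4.3.6.1 tabulates TEAE incidence "with safety subjects of that treatment group as the denominator, unless otherwise specified". Its list of tables includes a "General overview of TEAEs by 3 month periods", and no section gives that table a denominator of its own. The table is a firm plan, because SAP 4.3.1.6 writes date-imputation rules for it. The counting window is closed: events from first dose "until 30 days (inclusive) after the last dose of study drug will be considered treatment-emergent adverse events". SAP 4.1.4 defines the set as everyone dosed and adds: "For this single arm study, ITT and safety populations are identical". The general rule for categorical data in SAP 4.3.1.1 points the same way: "the percentages will be calculated of total number of patients in the set". The same section also keeps missing and not-done categories in the table.

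**Phlebotomies.** SAP 4.3.5.4 reads: "Number of phlebotomies during treatment phase will be summarized using descriptive statistics and frequency/percentage for categories of 0,1,2,3 and >3". Nothing is divided by time on treatment. Separately, SAP 4.3.4.2 and 4.3.5.5 plan a Kaplan-Meier analysis of time to first phlebotomy, censored at discontinuation.

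**Vascular and bleeding events.** SAP 4.3.4.2 lists "Proportion of subjects without thrombotic or hemorrhagic events" and stops there. It gives no follow-up requirement, no rule for patients who withdraw and no time-to-event analysis. SAP 4.3.1.5 plans no imputation.

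**Response, for contrast.** SAP 4.3.4.1 states that early withdrawal counts as non-response.

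**The concern.** A table by period is where a reader looks to see whether toxicity eases with time on drug. With a fixed denominator, a patient who stopped in Month 4 appears in Months 7–9 and 10–12 as someone treated without an adverse event. As w grows through the year the percentages drift down, even if the rate among patients still treated is constant. A single-arm trial has no control group subject to the same dilution.

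The later periods also matter clinically. On the schedule in Protocol 12.5, five steps of 50 µg take the dose from 100 to 350 µg at Week 10, and eight steps take it to 500 µg at Week 16. Protocol 12.1 notes the lack of experience above 300 µg in Japanese subjects. Some departures will be for toxicity (Protocol 12.5.2, 15.3.8 and 15.3.12), so the patients who remain are already selected for tolerance.

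The phlebotomy counts have a related weakness: six weeks with no phlebotomy falls in the same category as 52 weeks with none.

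**Working it through.** **Plan's own figure.** The plan gives none for these denominators. Its one power statement (about 85% at month 9 with 25 patients, SAP 2.4) does reproduce. Seven of 25 is the smallest count whose exact two-sided 95% lower limit exceeds 11%, and P(X ≥ 7 | n = 25, p = 0.36) = 0.852. It does not involve the denominators at issue.

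**Inputs.** N = 30 planned (SAP 2.4). The number no longer at risk, w, is not given for this trial and is assumed to be 0 to 6. The only completion count to hand is 217 of 254 in PROUD-PV (Protocol 5.3): 37/254 = 14.6%, and 0.146 × 30 ≈ 4.4. That count pools the P1101 and HU arms.

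**Period TEAE percentage.** Reported rate = at-risk rate × (N − w)/N.

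| w | Factor | True 50% reads | 8 patients with a TEAE: on N = 30 | Same 8, on those at risk |
|---|---|---|---|---|
| 0 | 30/30 = 1.000 | 50.0% | 26.7% | 26.7% |
| 2 | 28/30 = 0.933 | 46.7% | 26.7% | 28.6% |
| 4 | 26/30 = 0.867 | 43.3% | 26.7% | 30.8% |
| 6 | 24/30 = 0.800 | 40.0% | 26.7% | 33.3% |

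Read down the third column: if w were 0, 2, 4 and 6 in the four successive periods and the true rate a constant 50%, the table would fall from 50.0% to 40.0%.

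**Phlebotomy counts.** Assume a Poisson rate of 2 per year, with 4 of 30 leaving at month 6.
- Mean: (26 × 2 + 4 × 1)/30 = 1.87, against 2.00 with full follow-up (−6.7%).
- Zero category: (26 × e⁻² + 4 × e⁻¹)/30 = 16.6%, against e⁻² = 13.5%, about 3 points.
- With 2 to 6 leaving at months 3 to 9, the mean falls by 1.7% to 15%.

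**Thrombosis/hemorrhage-free proportion.** Assume a 12-month risk of 10% at constant hazard, with 4 leaving at month 3.
- If no recorded event counts as event-free: (26 × 0.90 + 4 × 0.90^0.25)/30 = (23.4 + 3.90)/30 = 91.0%, against 90.0%, so about 1 point too high. With 2 to 6 leaving at months 3 to 9 and risks of 5% to 20%, the excess is 0.1 to 2.9 points.
- If leavers go into a missing category but stay in N: 23.4/30 = 78.0%, which is too low.

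The sign depends on a rule that the SAP does not state.

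**The case against.** The best case for the plan runs as follows.

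- Whole-study TEAE incidence on all treated patients is conventional, and SAP 4.3.1.1 gives its reason: closeness to the intent-to-treat principle.
- The denominator sentence allows exceptions.
- No test or success rule uses these summaries.
- Readers also get disposition with reasons for discontinuation (SAP 4.3.2), a table of TEAEs leading to discontinuation, derived exposure (SAP 3.10.3) and full listings.

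All of this stands for whole-study incidence. It does not rescue the period table. No exception is written for it, and none of the other outputs supplies the number at risk in each period.

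On phlebotomies the objection is stronger. The planned Kaplan-Meier analysis of time to first phlebotomy already gives a follow-up-adjusted estimate of the proportion with none. What remains unadjusted is the mean count and the split above zero. A reader might take 4/30 = 13 points as the bias in the zero category. That is only the largest share of the category that four leavers could fill. Some of them would have had no phlebotomy anyway, and Protocol 14.1 calls for phlebotomy whenever hematocrit is 45% or higher, so some may have had one before leaving.

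On vascular events, a reader might infer that early leavers are counted as event-free. The SAP does not say so, and its missing category together with no imputation permits the opposite.

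The sizes all rest on assumed withdrawals. Protocol 5.6 calls dropout low in the PROUD-CONTINUATION-PV study.

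**Conclusion.** The point holds for the 3-month TEAE overview. If the SAP is followed as written, late-period percentages are understated by the factor (30 − w)/30: 0.933, 0.867 or 0.800 for an assumed w of 2, 4 or 6, and no effect at w = 0. The direction is one-sided, because time after the window closes can add to the denominator but never to the numerator.

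The phlebotomy counts share the weakness to a lesser degree, and the Kaplan-Meier analysis already covers the zero category. For the thrombosis/hemorrhage-free proportion the finding is an ambiguity. The effect is about 1 point in the example on the favourable reading, and the opposite sign is possible.

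Two stronger conclusions are tempting and are not supported. The first is that all three outcomes will look better than they are; the documents fix that direction only for the TEAE periods and the phlebotomy counts, and only if patients withdraw. The second is that any fall in the period table must come from patients leaving; a real decline is equally possible, and the planned table cannot tell the two apart.

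The primary CHR analysis and its power are untouched. The change is worth making before database lock but does not threaten the main conclusion.

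**What to change.** 1. **SAP 4.3.6.1, main change.** For the 3-month overview, define each period's denominator as the safety subjects still within the TEAE window (first dose to 30 days after last dose) at the start of the period, and show the patient-months observed in each period. Keep whole-study TEAE incidence on all safety subjects.
2. **SAP 4.3.5.4.** Beside the categories, add phlebotomies per patient-year, using the treatment period defined in SAP 3.6. Refer the reader to the Kaplan-Meier analysis for the proportion with none. Splitting the categories by completion status is unnecessary; about four leavers over five categories would give near-empty cells.
3. **SAP 4.3.4.2.** State how withdrawn patients count in the thrombosis/hemorrhage-free proportion, and report a Month 12 Kaplan-Meier event-free estimate beside it, censored at the last adverse event assessment.

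The cost is SAP wording and a few lines of programming. Dosing, adverse event and phlebotomy dates are already needed for other planned derivations, so no new data are collected. The downside is that late-period adverse event rates become slightly less favourable and rest on smaller denominators.

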4.3.6.2 Physical Examination

Results of physical examination by visit will be reported in frequency tables.

4.3.6.3 Vital signs, ECG parameters, Safety Laboratory data Lung X-Ray, Heart ECHO, and Ocular examination

Values out of normal ranges will be flagged in data listings. Laboratory values will be presented in conventional units. No formal statistical tests comparing results of vital signs and safety laboratory data will be performed.

Absolute values and changes from baseline will be descriptively analyzed by study visits. Count (and percentage) of values in the normal ranges, abnormal clinically significant and not clinically significant will be displayed in summary tables together with descriptive statistics.

In tables and listings all local and central assessment will be presented (and clearly distinguished). In figures local and central assessment will be presented separately.

For assessments without numeric result (e.g. result positive/negative, normal/abnormal) counts and percentages by visit will be presented in the tables and shift tables will be used for presentation of change between Screening and EOT visit/ V27.

4.3.6.4 Bone Marrow Assessment

The parameters of bone marrow assessment, which is an optional measurement in the study, will be listed.

4.3.6.5 Hospital Anxiety and Depression Scale (HADS) and ECOG performance status

Hospital Anxiety and Depression Scale (HADS) classifies an anxiety and a depression as follows: Normal/Mild/Moderate/Severe.

ECOG performance status is classified into 6 levels Grade 0 (Fully active) - Grade 5 (Dead). Descriptive analysis will include frequencies of patients with individual grades by visit.

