10. Hospital Anxiety and Depression Scale (HADS) score 0-7 on both subscales (Appendix 8).
  - (Patients with a borderline of HADS score (score  $> 7$  but  $<10$ ) or patients with necessity (expected benefits are higher than the risks) based on investigators' discretion are required to receive following assessment by psychiatric specialist to confirm the eligibility for IFN $\alpha$  therapy.)

11. Males and females of childbearing potential, as well as all women  $<2$  years after the onset of menopause, must agree to use an acceptable form of birth control until 28 days following the last dose of the study drug
12. Written informed consent obtained from the patient or the patient's legal representative, and ability for the patient to comply with the requirements of the study

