### **15.3.1.5 Hospital Anxiety and Depression Scale (HADS)**

The Hospital Anxiety and Depression Scale (HADS) will be used. HADS is a self-report questionnaire commonly used by doctors and therapists to assess levels of anxiety and depression in patients. The HADS comprises 14 statements which the patient rates based on their experience over the past week. Each question has 4 possible responses. Responses are scored on a scale from 3 to 0. The maximum score is 21 for depression and 21 for anxiety. A score of 11 or higher indicates the probable presence of mood disorder, with a score of 8 to 10 being just suggestive of the presence of the respective state. The HADS is divided into four ranges: normal (0-7), mild (8-10), moderate (11-15) and severe (16-21) (Snaith 2003). HADS was found to perform well in assessing the symptom severity and identifying cases of anxiety disorders and depression in both somatic, psychiatric and primary care patients and in the general population (Bjelland et al. 2002). HADS is being used and confirmed to be a valid tool for assessment of psychiatric side effects of interferon alpha (Kraus et al. 2005). Furthermore, the HADS can be administered by non-psychiatrist physicians (Olsson, Mykletun, and Dahl 2005). For HADS see Appendix 8.

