3.10.4 Interpretation of HADS scores

Total score of depression and anxiety is interpreted as follows:

- Score 0-7: Normal
- Score 8-10: Mild
- Score 11-14: Moderate
- Score 15-21: Severe

4 Statistical and Analytical Procedure

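### HADS is summarised only in four severity bands and entry normally puts every patient in the lowest one, so a group rise within 0–7 would not appear in a band table, and no within-patient change in score is specified.

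*SAP*

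**What the plan says.** - **Analysis.** The HADS-specific sentence in SAP 4.3.6.5 is "Hospital Anxiety and Depression Scale (HADS) classifies an anxiety and a depression as follows: Normal/Mild/Moderate/Severe". The section ends "Descriptive analysis will include frequencies of patients with individual grades by visit". That sentence follows the description of ECOG grades, so its application to HADS is inferred.
- **Bands.** SAP 3.10.4 opens "Total score of depression and anxiety is interpreted as follows", and its lowest band is "Score 0-7: Normal". The others are 8–10, 11–14 and 15–21.
- **Scale.** Protocol 15.3.1.5 states "The maximum score is 21 for depression and 21 for anxiety".
- **Entry.** Protocol 9.1, criterion 10, requires "Hospital Anxiety and Depression Scale (HADS) score 0-7 on both subscales (Appendix 8". Borderline scores, or cases the investigator judges necessary, may enter after assessment by a psychiatric specialist.
- **Timing.** Protocol 8 places HADS at screening and Months 3, 6, 9 and 12. Appendix 1 also marks the premature discontinuation visit and the safety follow-up. There is no Week 0 assessment, so screening is the baseline.
- **Change from baseline.** SAP 4.3.6 says "Change from baseline will be included in summary tables for laboratory, ECG, and vital sign parameters". The change and shift tables in SAP 4.3.6.3 sit under a heading that does not include HADS.
- **General rules.** SAP 4.3.1 lists everything in the database. SAP 4.3.1.1 gives n, mean, SD, median, quartiles and range for continuous data, without saying whether HADS scores count as continuous.

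**The concern.** The entry criterion and the lowest reporting band coincide. Nearly all patients therefore start in one category that covers 8 of the 22 possible scores. A patient going from 0 to 7 is tabulated as unchanged, while one going from 7 to 8 is tabulated as worse.

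This matters because psychiatric events are a named class of adverse events of special interest (Protocol 7.4). The protocol also justifies the instrument for this purpose: "HADS is being used and confirmed to be a valid tool for assessment of psychiatric side effects of interferon alpha". HADS is the only serial quantitative mood measure in the trial. With 30 patients and no control arm, each patient's own screening score is the natural reference, and the plan names no summary that uses it. The SAP does plan both category counts and changes from baseline for laboratory values and vital signs, and gives no reason for treating HADS differently.

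**Working it through.** **1. The plan's own figure.** Appendix 8 assigns 7 items to each subscale, each scored 0 to 3. The maximum is 7 × 3 = 21, which agrees with Protocol 15.3.1.5.

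**2. What a band table cannot show.** A patient who starts at b (0 to 7) can rise by 7 − b points and stay Normal: 7 points from 0, 5 from 2, 3 from 4. The number of distinct rises with both scores inside 0–7 is 7 + 6 + 5 + 4 + 3 + 2 + 1 = 28. None of them changes the table.

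**3. How many patients would leave Normal.** Suppose all 30 patients rise by d points. Those who cross are the ones with b + d > 7. For d = 2 these are baselines 6 and 7; for d = 3, baselines 5, 6 and 7. The plan gives no baseline distribution, so several are assumed: uniform on 0–7, and weights proportional to exp(−½((b − m)/2)²) on 0–7 for m = 2, 3, 4, 5.

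| Assumed baseline | Mean | Cross at d = 2 | Cross at d = 3 |
|---|---|---|---|
| m = 2 | 2.4 | 4% (1.2 of 30) | 11% (3.4) |
| m = 3 | 3.1 | 10% (2.9) | 22% (6.7) |
| m = 4 | 3.9 | 20% (5.9) | 38% (11.4) |
| m = 5 | 4.6 | 33% (10.0) | 56% (16.7) |
| Uniform | 3.5 | 2/8 = 25% (7.5) | 3/8 = 37.5% (11.25) |

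**4. What a change summary would show.** The 95% CI half-width for the mean change is 1.96 × SD/√n. With n = 30 and an assumed SD of change of 2, 3 or 4:

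- 1.96 × 2/√30 = 0.72
- 1.96 × 3/√30 = 1.07
- 1.96 × 4/√30 = 1.43

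A 2-point mean rise exceeds all three.

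**5. Illustration of the information lost.** Simulated trials of 30 patients used normal scores with mean 3 or 4, SD 2.5 and correlation 0.5 or 0.7. Scores were rounded and clipped to 0–21, patients were kept if the screening score was 7 or less, and every patient was shifted equally. The full score is judged by a paired t test at 5%. The bands are judged by an exact McNemar test. With no one starting above Normal, that test needs 6 crossings: 2 × 0.5⁶ = 0.031, whereas 5 give 2 × 0.5⁵ = 0.063.

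| True rise | Full score | Bands |
|---|---|---|
| 1 point | 64–87% | 1–19% |
| 1.5 points | 92–99% | 6–48% |
| 2 points | over 99% | 21–78% |

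At a 3-point rise the gap narrows to 1–20 percentage points. With no true shift, rejection is 5.6–6.8% for the t test and 0–1% for the bands. Mean change is then about +0.1 to +0.2 points, from regression to the mean after selection on 0–7.

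**The case against.** A reader might infer that a rise below the cut-off is shown nowhere. The documents do not support that. SAP 4.3.1 lists all database data, so with 30 patients a listing of scores shows each individual rise. SAP 4.3.1.1 can be read to give by-visit means, and a rising mean would then be visible. SAP 4.3.6.5 describes a classification; it does not say the scores are discarded. SAP 4.3.6 names change from baseline for three data types without excluding others.

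A reader might also infer that the trial would give false reassurance, with nearly everyone Normal while mood worsens. That goes too far:

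- In the model of step 5, a 2-point rise puts about 4 to 7 of 30 patients at 8 or above at a single visit, which a reader of the table would notice.
- Psychiatric events are also collected as adverse events and AESIs at two-weekly visits.
- HADS is not a listed endpoint in Protocol 7 or SAP 2.3, and the documents give no threshold for a meaningful change within 0–7.

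The power comparison has limits too. The SAP plans no HADS test, all the inputs are assumed, and an equal shift in every patient favours the full score. If only 6 of 30 patients worsen by 8 points, the same setup gives the t test 67–83% and the bands 72–94%. And if everyone starts Normal, the count at 8 or above is already a within-patient crossing count, apart from dropouts and patients admitted under the exception.

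All of this stands, and it reduces the concern to a missing summary. It does not supply one. Listings do not summarise a group shift, the continuous-data rule is never tied to HADS, and neither provides within-patient change.

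**Conclusion.** The point holds in limited form. The HADS-specific analysis is four bands, and entry normally places every patient in the lowest. A group-level rise within 0–7 would not appear in a band table. It could be seen in listings or, on one reading of a general rule, in by-visit means. Within-patient change in score is not specified anywhere.

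As to size, a uniform 2-point rise would move about 1 to 10 of 30 patients out of Normal, while a mean change would be estimated to within about 0.7 to 1.4 points. These ranges rest on assumed baseline distributions and an assumed SD of change. The detection percentages further assume an equal shift in all patients and tests the plan does not contain, so they illustrate lost information and are not a power claim about this trial. The conclusion is that the SAP can be improved cheaply. Nothing here shows that a psychiatric signal would be missed.

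**What to change.** In SAP 4.3.6.5, keep the band table and state that it applies to HADS by visit. For the anxiety and depression subscales separately, add:

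- by-visit descriptive statistics of the score;
- within-patient change from screening at Months 3, 6, 9 and 12, premature discontinuation and follow-up (n, mean, SD, median, range, 95% CI of the mean change).

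Add HADS to the change-from-baseline parameters in SAP 4.3.6. Footnote that selecting on 0–7 produces some regression to the mean, about 0.1–0.2 points under the assumptions above.

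Do not tabulate the mean of each patient's largest on-treatment increase. Over four visits it averages about 1.4–2.0 points with no true change, and in an uncontrolled trial that can look like harm. If it is wanted, give it as a listing with a note that it is positive by construction.

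Two adjacent wording points can be settled in the same edit. SAP 3.10.4 speaks of a total score and should say that each subscale is banded separately. A score of 15 is Moderate in Protocol 15.3.1.5 but Severe in SAP 3.10.4, and the two must be reconciled.

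The cost is a few lines of SAP text and one table from scores already collected, with no extra visits or patients.
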